3.3. Dose-Limiting Toxicity Evaluation and Determination of RP2D

For the Phase 1b erdafitinib + cetrelimab cohort, refer to Section [3.3](#) of Appendix 1. For the Phase 1b erdafitinib + cetrelimab + platinum chemotherapy cohort, refer to Section [3.3](#) of Appendix 2.

3.3.1. Definition of Dose-Limiting Toxicity for Phase 1b (Dose Escalation)

For the Phase 1b erdafitinib + cetrelimab cohort, refer to Section [3.3.1](#) of Appendix 1. For the Phase 1b erdafitinib + cetrelimab + platinum chemotherapy cohort, refer to Section [3.3.1](#) of Appendix 2.

3.3.2. Determination of the Phase 1b RP2D Regimen and Alternative Dosing Schedules

For the Phase 1b erdafitinib + cetrelimab cohort, refer to Section 3.3.2 of Appendix 1. For the Phase 1b erdafitinib + cetrelimab + platinum chemotherapy cohort, refer to Section 3.3.2 of Appendix 2.

3.4. Study Evaluation Team

Subject safety will be monitored throughout the Phase 1b part of the study by the SET established by the sponsor until the RP2D of erdafitinib and cetrelimab is determined. This committee will monitor all available treatment-emergent data (eg, PK, PD, safety) on an ongoing basis throughout the study to ensure the safety of subjects enrolled in this study.

The SET will be chaired by the sponsor's Molecule Responsible Physician and membership will include the sponsor Study Responsible Physician, a sponsor clinical scientist, a subset of the study principal investigators, safety physician (sponsor's Safety Management Team chair), statistician, and clinical pharmacologist, along with additional sponsor staff, as appropriate. The team will meet at regular frequency throughout study conduct. In addition, SET meetings may be conducted at any time during the study at the request of either the sponsor or investigator(s) to assess emerging safety signals. Documentation of meeting outcomes will be maintained by the sponsor. Decisions will be communicated to investigators and decisions with the potential to affect subject safety (eg, unfavorable change in benefit/risk assessment) will also be promptly communicated to regulatory authorities as required.

Dose escalation decisions in Phase 1b of the study will be made by the SET. The schedule of dose escalation meetings will depend on the frequency of DLTs and if/when the MTD or maximum administered dose is determined or when an RP2D is determined. The SET can evaluate up-titrated and non-up-titrated subjects separately based on the totality of the emerging safety data. Cumulative safety data will be routinely assessed by the DRC after the RP2D of erdafitinib and cetrelimab is determined.

Prior to the determination of the RP2D of erdafitinib and cetrelimab, the SET may also decide on modifications in study conduct such as additional dose cohorts/dose levels if required or stop further enrollment into 1 or more of the cohorts/dose levels if treatment-emergent toxicity is determined to result in an unfavorable change in subject risk/benefit. Enrollment may be temporarily held, if needed, for the SET to evaluate the emerging data.

4. SUBJECT POPULATION

For the Phase 1b part of the study, refer to Section 4 of Appendix 1 or Section 4 of Appendix 2, as appropriate.

For the Phase 2 cohort of the study, refer to Section 4 of Appendix 3.

5. TREATMENT ALLOCATION AND BLINDING

For the Phase 1b part of the study, refer to Section 5 of Appendix 1 or Section 5 of Appendix 2, as appropriate.

For the Phase 2 cohort of the study, refer to Section 5 of Appendix 3.

6. DOSAGE AND ADMINISTRATION

For the Phase 1b part of the study, refer to Section 6 of Appendix 1 or Section 6 of Appendix 2, as appropriate.

For the Phase 2 cohort of the study, refer to Section 6 of Appendix 3.

6.1. Dose Combination Cohorts/Arms

For the Phase 1b part of the study, refer to Section 6.1 of Appendix 1 or Section 6.1 of Appendix 2, as appropriate.

For the Phase 2 cohort of the study, refer to Section 6.1 of Appendix 3.

6.2. Administration of Erdafitinib

Erdafitinib will be provided as tablets for oral administration. The study drug is to be taken with approximately 240 mL (8 ounces) of water. The tablets should be swallowed intact and subjects should not attempt to dissolve them in water. Each dose should be taken at approximately the same time each day in the morning with or without food. Should an alternative dosing schedule be used in the study, subjects will be instructed to take their assigned dose of the study drug orally on that alternative dosing schedule.

The study drug will be dispensed at the first visit of each cycle. All study drug doses dispensed must be captured in the source documents, including the subject's diary card, and the electronic case report form (eCRF). Unused study drug in the issued bottles and empty bottles must be returned to the site at each study visit. Study drug must be returned to the site when a subject discontinues study treatment. Returned tablets cannot be re-issued in this study or outside the study (follow study drug accountability guidelines in the Site Investigational Product and Procedures Manual [SIPPM]).

If a dose is missed, it can be taken up to 6 hours after the scheduled time; the subject may return to the normal schedule the following day. If it has been more than 6 hours since the missed dose, then that dose should be skipped and the subject should continue treatment at the scheduled time the next day. Missed doses will not be replaced and the next dose will remain unchanged. If vomiting occurred with drug administration, no replacement dose will be taken and any such event that occurs up to 4 hours following dose administration must be recorded on the subject's diary card and the eCRF.

6.2.1. Dose Up-titration Guidelines

Based on emerging safety data, on 12 May 2020, the DRC recommended to remove the requirement for up-titration from the erdafitinib + cetrelimab combination in Arm B. The DRC also made a recommendation to close Dose level 2 in Phase 1b and focus enrollment efforts into the Phase 2 part of the study. Therefore, DL2 will be closed. DL2B will remain open and will include up-titration of erdafitinib based on serum phosphate concentration from a blood sample on Day 15 and the absence of significant erdafitinib-related toxicity on C1D15 as determined by the investigator.

Subjects assigned to Dose Level DL2 or DL2B in Phase 1b or Arm A and in Phase 2, will be assigned to the up-titrated dose level of erdafitinib based on serum phosphate concentration from a blood sample on Day 15 and the absence of significant erdafitinib-related toxicity on C1D15 as determined by the investigator. There is no up-titration in either of the erdafitinib + cetrelimab + platinum (cisplatin or carboplatin) chemotherapy cohort or Arm B of the Phase 2 erdafitinib +/- cetrelimab cohort.

- Subjects with serum phosphate levels higher than 9.00 mg/dL (>2.91 mmol/L) will withhold erdafitinib treatment, with at least weekly assessment of serum phosphate levels until it returns to less than 7.00 mg/dL (<2.25 mmol/L) while initiating treatment with a phosphate binder such as sevelamer (see [Table 8](#) for detailed guidelines regarding further treatment).
- Subjects with serum phosphate levels between 7.00 to 8.99 mg/dL (2.25 mmol/L to 2.90 mmol/L) should increase the erdafitinib dose to 9 mg once daily, while concurrently initiating treatment with a phosphate binder such as sevelamer (see [Table 8](#) for details).
- Subjects with serum phosphate level less than 7.00 mg/dL (<2.25 mmol/L) will increase the erdafitinib dose to 9 mg once daily without concomitant phosphate binder such as sevelamer.

6.2.2. Dose Modification, Dose Delays, and Retreatment Criteria for Erdafitinib

Treatment with erdafitinib should be discontinued or modified based on toxicity as described in [Table 5](#) and the specific guidance below. For eye, skin/nail, dry mouth/mucositis, liver, and phosphate toxicities, specific management guidelines are provided in Sections [6.2.3.1](#) through Section [6.2.3.7](#). This guidance is only intended for toxicity management.

Table 5: Erdafitinib Dose Modification Rules Based on Toxicity ^a

Toxicity Grade	Action	Dose modification after resolution of AE
1	None	Continue same dose.
2	None or consider interruption if the toxicity is considered clinically significant	If interrupted, restart at same dose if toxicity is completely resolved to baseline or consider restarting at 1 dose lower ^b if not completely resolved to baseline (but resolved to Grade 1).
3	Interrupt drug	Restart at 1 dose lower ^b if recovered to baseline (to Grade ≤ 1 or back to baseline for non-hematologic toxicity) within 28 days; restart at 2 doses lower ^b if not completely resolved to baseline (but resolved to Grade 1). Discontinue drug if unresolved for >28 days.
4	Interrupt drug	Discontinue.

Abbreviations: AE = adverse event

^aFor eye, skin/nail, dry mouth/mucositis, liver, and phosphate toxicity please follow specific recommendations in the management guidelines.

^b Please refer to [Table 6](#).

- Subjects with any Grade of toxicity (Grade 1 to 4) should be provided symptomatic treatment where applicable.
- If erdafitinib is interrupted consecutively for 1 week or longer due to drug-related toxicity, the study drug may be reintroduced at either the same dose level or the first reduced dose level following recovery from the toxicity ([Table 6](#)). A second dose reduction may be implemented following a second occurrence of drug-related toxicity.
- If erdafitinib must be withheld for more than 28 days for a drug-related AE that fails to resolve to acceptable level (eg, Grade ≤ 1 non-hematologic toxicity or back to baseline), treatment with erdafitinib should be discontinued except when the subject has been deriving benefit from treatment, and the investigator can demonstrate that re-introduction of erdafitinib is in the best interest of the subject. Erdafitinib may be reintroduced at the same or a lower dose ([Table 6](#)) if the medical monitor is in agreement with the assessment.
- If erdafitinib was dose-reduced and the AE that was the reason for this dose reduction has completely resolved, the dose may be re-escalated to the next higher dose when the subject has been deriving benefit from treatment, and the investigator can demonstrate that dose re-escalation of erdafitinib is in the best interest of the subject and the medical monitor is in agreement with the assessment.
- In all cases of clinically significant impaired wound healing or imminent surgery or potential bleeding complications, it is recommended that dose administration be interrupted, appropriate clinical laboratory data (eg, coagulation) be carefully monitored, and supportive therapy administered, where applicable. Dose administration may be restarted when it is considered safe and at an appropriate dose, according to the investigator's assessment.

Dose modification rules are provided in [Table 6](#).

Table 6: Dose Schedule and Dose Reductions for Erdafitinib

Category	No up-titration		With up-titration
	Dose	Dose	Dose
Starting dose	6 mg	8 mg	8 mg
Up-titration	None	None	9 mg
1st dose reduction	5 mg	6 mg	8 mg
2nd dose reduction	4 mg	5 mg	6 mg
3rd dose reduction	stop	4 mg	5 mg
4th dose reduction		stop	4 mg
5th dose reduction			stop

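### Section 6.2.2: after a single drug-related Grade 3 event that stops erdafitinib for a week or more, Table 5 requires a lower restart dose, the second bullet permits the same dose, and no precedence is stated

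*Protocol*

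**What the plan says.** The opening sentence of Protocol Section 6.2.2 bases erdafitinib modification on Table 5 "and the specific guidance below". The bullets under the table belong to that guidance.

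- **Table 5, Grade 3 row.** Interrupt the drug. Restart 1 dose lower if the event has recovered to baseline, which the table glosses as Grade 1 or less "or back to baseline for non-hematologic toxicity) within 28 days". The second branch, 2 doses lower, applies "if not completely resolved to baseline (but resolved to Grade 1). Discontinue drug if unresolved" for more than 28 days. The row has no same-dose option.
- **Table 5, Grade 2 row.** If dosing was interrupted, restart at the same dose when fully resolved, "or consider restarting at 1 dose lower" when resolved only to Grade 1.
- **Second bullet.** After a drug-related interruption of at least 1 week, "the study drug may be reintroduced at either the same dose level or the first reduced dose level following recovery from the toxicity". It continues: "A second dose reduction may be implemented following a second occurrence of drug-related toxicity".
- **Third bullet.** After more than 28 days off drug without adequate recovery, treatment normally stops. As an exception, "Erdafitinib may be reintroduced at the same or a lower dose", provided the medical monitor agrees.
- **Fourth bullet.** Re-escalation after a reduction also needs medical monitor agreement.
- **Footnote a of Table 5.** It sends certain organ toxicities elsewhere: for eye, skin/nail, dry mouth/mucositis, "liver, and phosphate toxicity please follow specific recommendations in the management guidelines".

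Section 6.5 tells sites to take the strictest adjustment when recommendations conflict, on the condition that the subject has several toxicities.

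**The concern.** The second bullet is triggered by attribution (drug-related) and duration (a week or more), not by grade. Many Grade 3 events that take a week to settle will meet both conditions. For those events the section gives two different sets of permitted restart doses and does not say which governs.

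A site that takes the bullet at its word can put a subject back on the dose at which a drug-related Grade 3 toxicity occurred, without consulting the medical monitor. A site that takes Table 5 at its word cannot. Section 6.2.2 serves Phase 1b and both Phase 2 arms. Appendix 4 still directs sites to Section 6.2 for subjects who stay on treatment after Amendment 5.

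**Working it through.** The section states no statistical figure on this point, so the check is a comparison of rules followed by the dose ladder in Table 6.

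**1. Which events fall under both rules.** Three conditions must hold together:
- the event is Grade 3 (Table 5);
- it is drug-related and interrupts erdafitinib for 1 week or longer (second bullet);
- Section 6.2.3 gives no restart dose for it.

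Grade 3 phosphate, dry mouth, mucositis, dry skin, nail, paronychia and vision-related eye events are outside, because Tables 8 to 14 give their restart dose. Diarrhea is an example inside. Liver toxicity is named in Section 6.2.2 as having its own guideline, but Sections 6.2.3.1 to 6.2.3.7 contain none. For interruptions shorter than a week, Table 5 stands alone.

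**2. What each rule permits for such an event.**
- Table 5, Grade 3: 1 dose lower, or 2 doses lower.
- Second bullet: the same dose, or the first reduced dose.

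The same-dose option is in the bullet only.

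**3. Whether anything ranks them.**
- The opening sentence joins table and bullets with "and" in effect: "and the specific guidance below". No order is given.
- Footnote a yields only to the organ guidelines, not to the bullets.
- The first bullet speaks of Grades 1 to 4, so the list is not confined to low grades.
- Section 6.5 requires several toxicities, so it does not decide a single event.

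**4. Dose difference after a first event (Table 6).**
- 8 mg without up-titration (for example Arm B): first reduction 6 mg. Same dose against 1 lower is 8/6 = 1.333, so 33.3% higher.
- 9 mg after up-titration (for example Arm A): first reduction 8 mg. 9/8 = 1.125, so 12.5% higher.

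**5. How the same-dose option compares with the other Grade 3 rules.**
- Dry mouth, mucositis, dry skin, nail toxicity and paronychia (Tables 9 to 13): 1 dose level lower, in consultation with the medical monitor.
- Vision-related eye toxicity (Table 14): 2 levels lower, with investigator and medical monitor in agreement.
- Phosphate (Table 8): same dose, but stated expressly for that toxicity.
- Grade 3 or higher events attributable neither to study treatment nor to the disease (Section 6.1 of Appendices 1 and 3): erdafitinib restarts one level lower.

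Taken literally, the bullet is therefore more lenient towards a drug-related Grade 3 event than Appendices 1 and 3 are towards an unrelated one.

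**The case against.** The strongest reply is that the two rules can be satisfied together. Table 5 is directive for Grade 3, and the bullet only says what a site may do. After a recovered Grade 3 event, exactly one dose meets both: 1 dose lower. The bullet's same-dose option then serves Grade 2, whose row offers the same pair of choices. The rest of the protocol leans the same way. Apart from phosphate, Grade 3 restart rules call for a reduction, and Section 6.5 shows that doubt is to be resolved conservatively.

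This is a plausible account of the intent, and a careful site may well act on it. It is not what the text says. The bullet has no grade limit and names the same dose as an option in its own right, so a same-dose restart would be hard to call a deviation.

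A reader might go further and infer that the two rules leave no common dose, since Table 5 can require 2 doses lower (5 mg from 8 mg) while the bullet offers 8 mg or 6 mg and links a second reduction to a second occurrence. That is not established. The bullet applies only after recovery, and the 2-dose branch is for events not fully resolved. The clash arises only if settling at Grade 1 counts as recovery under the bullet. The gloss in the first branch of Table 5 suggests that a non-hematologic event at Grade 1 belongs in the 1-dose branch anyway.

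It is also fair to say that few dosing decisions may remain once subjects move to the reduced schedule under Amendment 5.

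**Conclusion.** The point holds for a defined set of events: a single drug-related Grade 3 toxicity, an interruption of 1 week or longer, and no restart dose in Section 6.2.3. There Table 5 requires at least 1 dose lower, the second bullet permits the same dose without medical monitor agreement, and the protocol states no precedence. For a first event the gap is 8 mg against 6 mg, or 9 mg against 8 mg. The conclusion assumes that the bullet means what it says and is not silently limited to Grade 2.

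Two larger claims might be inferred and are not supported. The counts of drug-related Grade 3-4 events in the earlier erdafitinib study (Section 1.3, Table 2) are not the share affected: they include Grade 4 events and events with their own guideline, and they do not record how long dosing was interrupted. The share cannot be derived from the protocol. Nor is a restart at 4 mg, where Table 6 would next say stop, a first-event case, because 4 mg is reached only after earlier reductions.

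This is a matter of consistent dosing and subject safety that should be corrected. No sample size, error rate or analysis is affected.

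**What to change.** Amend the second bullet of Section 6.2.2 so that, after a drug-related interruption of 1 week or longer, the restart dose follows Table 5 for the grade of the event, or the Section 6.2.3 guideline where that gives a restart dose (for example Table 8 for Grade 3 phosphate). Align its second sentence so that any further reduction follows the same rule. Leave unchanged the Grade 2 row, Grade 4 discontinuation, the more-than-28-day exception and the re-escalation bullet. The Grade 3 branches of Table 5 also stay as they are; narrowing the 2-dose branch would be a clinical decision and would remove a stricter option.

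The drafting cost is a short rewording of one bullet. The clinical cost is that some Grade 3 restarts will be one level lower than a site might have chosen. That works somewhat against the dose intensity the Data Review Committee sought when it recommended removing up-titration from Arm B. Re-escalation with medical monitor agreement remains available once the event has fully resolved.

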6.2.3. Guidance for Specific Erdafitinib Toxicities

Guidance related to specific erdafitinib toxicities is discussed in this section.

6.2.3.1. Grading of Hyperphosphatemia and Nail Disorders

Hyperphosphatemia and AEs related to nails will be graded as outlined in [Table 7](#).

Table 7: Grading of Hyperphosphatemia and Nails Adverse Events

Adverse Event	Grade 0	Grade 1	Grade 2	Grade 3	Grade 4
Nail Changes (onychodystrophy)		Nail discoloration, asymptomatic separation of the nail bed from the nail plate or nail loss	Nail/fingertips pain, symptomatic separation of the nail bed from the nail plate or nail loss; limiting instrumental ADL	Severe nail fingertips pain, symptomatic separation of the nail bed from the nail plate or nail loss; significantly limiting instrumental ADL	Life-threatening consequences, urgent intervention indicated
Hyperphosphatemia	<5.50 mg/dl <1.75 mmol/L	5.50-6.99 mg/dl 1.75-2.24 mmol/L	7.00-8.99 mg/dl 2.25-2.90 mmol/L	9.00-10.00 mg/dl (2.91-3.20 mmol/L), or asymptomatic soft tissue calcification with any phosphate level	>10.00 mg/dl >3.20 mmol/L, or symptomatic soft tissue calcification with any phosphate level

ADL= activities of daily living

6.2.3.2. Guidelines for the Management of Elevated Phosphate Levels

Guidelines for the clinical management of elevated serum phosphate levels are presented in [Table 8](#).

Table 8: Guidelines for Management of Serum Phosphate Elevation

Serum Phosphate Level	Study Drug Management	Symptom Management
<5.50 mg/dL (<1.75 mmol/L) (Grade 0)	Continue erdafitinib treatment.	None.
5.50-6.99 mg/dL (1.75-2.24 mmol/L) (Grade 1)	Continue erdafitinib treatment.	Restriction of phosphate intake to 600 – 800 mg/day.
7.00-8.99 mg/dL (2.25-2.90 mmol/L) (Grade 2)	Continue erdafitinib treatment. A dose reduction will be implemented for persistent ^a hyperphosphatemia (defined as serum phosphate ≥7.00 mg/dL for a period of 2 months) or if clinically necessary (eg, in the presence of additional adverse events linked to hyperphosphatemia or electrolyte disturbances).	Restriction of phosphate intake to 600 – 800 mg/day. Start sevelamer 800 to 1,600 mg TID with food until phosphate level is <7.00 mg/dL.
9.00-10.00 mg/dL (2.91-3.20 mmol/L) (Grade 3)	Withhold ^b erdafitinib treatment until serum phosphate level returns to <7.00 mg/dL (weekly testing recommended). Restart treatment at the same dose level. A dose reduction will be implemented for persistent ^a hyperphosphatemia (defined as serum phosphate ≥9.00 mg/dL for a period of 1 month) or if clinically necessary (eg, in the presence of additional adverse events linked to hyperphosphatemia or electrolyte disturbances).	Restriction of phosphate intake to 600 – 800 mg/day. Sevelamer up to 1,600 mg TID with food until serum phosphate level returns to <7.0 mg/dL.
>10.00 mg/dL (>3.20 mmol/L) (Grade 4)	Withhold ^b erdafitinib treatment until serum phosphate level returns to <7.00 mg/dL (weekly testing recommended). Restart treatment at the first reduced dose level. If persistent ^a hyperphosphatemia (≥10.00 mg/dL) for >2 weeks, erdafitinib should be discontinued permanently.	Medical management as clinically appropriate.
Significant alteration in baseline renal function or Grade 3 hypocalcemia	Erdafitinib should be discontinued permanently. (In situations where the subject is having clinical benefit and the investigator and the sponsor's medical monitor agree that continuation of treatment is in the best interest of the subject, the drug may be restarted at 2 dose levels lower if appropriate. Follow other recommendations described above, Section 6.2.2.)	Medical management as clinically appropriate.

Abbreviations: TID = 3 times a day

Note: These are general guidelines that are based on emerging data and consensus experience of participating investigators or the experts in the field. The treating physicians must use clinical judgment and local standard of care to decide the best way to manage phosphate elevation. If sevelamer hydrochloride (Renagel[®]) is not available, use of other phosphate binders (non-calcium containing) based on the local standard is recommended, including sevelamer carbonate (Renvela) or lanthanum carbonate (Fosrenol[®]). These guidelines will be updated based on emerging data. Additional information on phosphorus in foods by class of food can also be found at www.permanente.net/homepage/kaiser/pdf/42025.pdf. Additional information for phosphate management and diet can be found at the National Kidney Foundation website (<http://www.kidney.org/atoz/content/phosphorus.cfm>)

a. Persistent hyperphosphatemia is considered to be more than 1 sequential phosphate value above the cutoff.

b. Study drug interruptions for hyperphosphatemia suggested to be 7 days in duration.

